8.2 Setting

8.2.1 Study Population

The study population will comprise the target audiences for the RM tools (HCPs and patients / caregivers) in markets where ABILIFY[®] for use in the adolescent bipolar I mania indication has been marketed for at least six months.

The study population will go through a pre-screening process as a component of the recruitment process. This is further described in the following section. If Ethics approval is needed for any specific country, this will be done through an appropriate principal investigator from that country, who may also take part in the survey if randomised alongside all other participants.

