PASS INFORMATIONENCEPP/SDPP/6083

Observational Study Protocol 31-13-300

Please note parts of the protocol including annexes have been currently redacted to avoid any bias to the study. The full protocol and annexes will be available when the study concludes.

Title	ABILIFY® for the Adolescent Bipolar I Mania
	Indication Tool Effectiveness Evaluation Survey
Protocol version identifier	Draft 5.0
Date of last version of protocol	15 October 2013
EU PAS register number	Study not registered
Active substance	Aripiprazole
	Antipsychotics
	ATC code: NO5AX12
Medicinal product	ABILIFY®
Product reference	PRD640634
	PRD640635
	PRD640636
	PRD640637
	PRD640638
	PRD640639
	PRD640640
	PRD640641
	PRD640642
	PRD640643
	PRD640644
	PRD640645
	PRD640646
	PRD640647
	PRD640665
	PRD640648
	PRD640649
	PRD640650
	PRD640651
	PRD640652
	PRD640653
	PRD640654

	DDDC40655	
	PRD640655	
	PRD640656	
	PRD640657	
	PRD640658	
	PRD28189	
	PRD640659	
	PRD640660	
	PRD640661	
	PRD640662	
	PRD640663	
	PRD640664	
Procedure number	EMEA/H/C/000471	
Marketing authorisation holder(s)	Otsuka Pharmaceutical Europe Ltd.	
Joint PASS	No	
Research question and objectives	The key research questions are:	
	1. What is the distribution of education material	
	across the markets?	
	2. What is the usage of the RM tools by HCPs	
	and patients / caregivers?	
	3. Do HCPs and patients / caregivers understand:	
	a. the information presented in the RM	
	tools, including	
	b. the indicated age range,	
	c. indicated dose,	
	d. duration of treatment before	
	prescribing ABILIFY	
	e. the identified and potential risks of	
	concern (extrapyramidal symptoms	
	(EPS), weight gain, somnolence,	
	fatigue) associated with ABILIFY for	
	adolescent bipolar I mania indication	
	4. Do HCPs and patients / caregivers respond	
	appropriately to hypothetical risk scenario	
	based questions regarding the clinical use of	
	ABILIFY for the adolescent bipolar I mania	
	indication, the identified and potential risks,	
	and the real-world usage, specifically the	

	recommended starting dosage, and minimum
	recommended age of patients
	The primary objectives of the study are to:
	1. To determine the proportion of HCPs, patients
	and caregivers that are aware of the RM tools
	and how the tools are accessed.
	2. To determine when, how and by whom the
	tools are used.
	3. To determine the level of knowledge and
	comprehension of the key risks associated with
	ABILIFY® when used for the treatment of
	paediatric bipolar I mania.

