7.2 Objectives

The concept of evaluation of the effectiveness of RM plans is defined by EU guidance: Module XVI⁽¹⁾ and Module XVI B.B11.4⁽¹⁾.

Effectiveness, for the purposes of this study, is defined as a combination of effective distribution, usage, knowledge, and adoption of appropriate stakeholder behaviours by HCPs, patients and caregivers.

The objectives of the survey are to evaluate the effectiveness of $ABILIFY^{\circledast}$ RM tools in markets where the adolescent bipolar I mania indication has been approved, and where $ABILIFY^{\circledast}$ has subsequently been prescribed in this indication for at least 6 months.

The surveys will provide information from HCPs (see Annex 1), and patients (see Annex 2) and caregivers (see Annex 3) on:

- 1. Distribution of the RM tools
- 2. Awareness and usage of the RM tools
- 3. Knowledge and comprehension of the key important identified risks
- 4. Behavioural responses to hypothetical risk scenarios
- 5. Minimisation of inappropriate starting dose and patient age

The evaluation is planned to be performed 12 months after implementation of the educational measures, in up to 13 EU member states (where usage of aripiprazole in paediatric patients is highest), to allow sufficient time for use and experience of the materials to conduct a meaningful assessment.

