8.2.4 Exclusion Criteria

HCPs will be excluded from the survey if they are not involved in the treatment of patients using ABILIFY for the adolescent bipolar I mania indication.

Protocol Number: 31-13-300 ABILIFY®

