9 PROTECTION OF HUMAN SUBJECTS

9.1 Ethics Committee Review and Informed Consent

9.1.1 Ethics Committee Review

This protocol will be submitted for review by ethics committees in each country wherein the study will be conducted, and the relevant national ethics committee will decide if any waiver applies.

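### A country principal investigator who takes the study through ethics review may also be a survey respondent: a small, conditional upward bias that one sentence would remove

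*Protocol*

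**What the plan says.** Section 8.2.1 provides that, if a country needs ethics approval, "this will be done through an appropriate principal investigator from that country". It then adds that this is someone "who may also take part in the survey if randomised alongside all other participants". Section 9.1.1 states what goes to the committees: "This protocol will be submitted for review by ethics committees in each country wherein the study will be conducted", with each national committee deciding whether a waiver applies.

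Section 8.2.4 contains one exclusion: "HCPs will be excluded from the survey if they are not involved in the treatment of patients" on this product for this indication. A PI who treats such patients stays eligible.

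Section 7.2 identifies the questionnaires as annexes to the protocol: "The surveys will provide information from HCPs (see Annex 1), and patients (see Annex 2) and caregivers (see Annex 3) on" the listed topics. The note on the title page explains why they are held back from the public version: "Please note parts of the protocol including annexes have been currently redacted to avoid any bias to the study". The contents entry for section 13 gives the same reason.

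**The concern.** The survey measures what HCPs know and whether they are aware of the tools after routine distribution. The protocol treats prior sight of its own content as a threat to that measurement. It withholds the annexes, and section 8.4 requires a single sitting with a time-out so that respondents cannot prepare or look up answers. Section 8.2.1 nevertheless admits a respondent who has handled the study documents beforehand.

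The condition attached, that the PI be randomised with everyone else, addresses a different problem. Section 8.2.2 uses random selection to stop particular HCP groups being favoured. That controls who enters the sample, not what a selected person already knows. The single-sitting rule acts only during the session, and the limitations in section 8.6 do not mention this route.

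Awareness and knowledge are primary endpoints 1 and 3 in section 8.1. The country samples are 12 or 13 HCPs, so one respondent carries visible weight. Any error of this kind runs in one direction, favouring the tools, and a confidence interval does not reflect it.

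**Working it through.** **What the PI has been exposed to**

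- *Follows from the text.* The protocol is the ethics submission (9.1.1) and the PI is the channel for approval (8.2.1). Its body describes both tools, the indicated age and treatment duration, and the four key risks (section 6), and lists the desired HCP behaviours (7.2.1). The visible text gives no dose figure, so it would not by itself supply an answer on dose.
- *Inferred only.* The HCP questionnaire is Annex 1 (7.2), so the PI may have seen it. No section says that the annexes reach the PI.

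**Inputs**

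- HCPs per country: 13 in six country rows, 12 in six (8.5).
- Planned proportion correct: p = 0.85; UK HCP population N = 2188; 95% confidence (8.5).
- Coverage of active prescribers: 20 to 30% (8.2.2), used as a rough chance that a given PI is included.
- Assumed for illustration, not in the protocol: p = 0.70 and p = 0.50.

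**The plan's own figure**

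Margin of error = 1.96 × √(0.85 × 0.15 / 13) × √((2188 − 13) / (2188 − 1)) = 19.36%, which agrees with section 8.5. The quotas sum to 6 × 13 + 6 × 12 = 150, inside the stated 148 to 158.

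**Shift if the PI is included**

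One PI is 1/13 = 7.7% or 1/12 = 8.3% of a country's HCP sample. If the PI answers correctly with certainty and the other respondents with probability p, the expected country proportion rises by ((n − 1)p + 1)/n − p = (1 − p)/n.

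| p | n = 13 | n = 12 |
|---|---|---|
| 0.85 (planned) | 1.2 points | 1.25 points |
| 0.70 (assumed) | 2.3 points | 2.5 points |
| 0.50 (assumed) | 3.8 points | 4.2 points |

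**Weighted by the chance of inclusion, at p = 0.85**

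- Low: 0.20 × 0.15/13 = 0.23 points.
- High: 0.30 × 0.15/12 = 0.375 points.

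So the expected shift is about 0.2 to 0.4 points per country. In a large pool it is smaller still. If all 2188 UK HCPs were on the list with equal chances, the first target list of 50 (8.2.2) would contain the PI with probability 50/2188 = 2.3%.

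**Upper bound across the study**

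One PI in each of the 12 country rows would be 12/150 = 8% of HCP respondents. The pooled shift would be 12 × (1 − p)/150: 1.2 points at 0.85 and 4.0 points at 0.50. This requires every country to need a PI and every PI to be drawn and to respond.

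**The case against.** The strongest case on the other side is that the effect hardly matters. Ethics approval must be needed, the PI must be on the list, be drawn, agree and complete the survey. Even with inclusion certain, 1.2 points is about one-sixteenth of the 19.36-point margin of error. The calculation also assumes that the PI would otherwise have answered like an average HCP, although a specialist chosen as PI might have scored well anyway. All of this stands, and it sets the severity.

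Second, the PI is not the only respondent with advance notice. Under section 8.2.2 the invitation letters set out the study objectives, and the lists take account of HCPs known to have been provided with the tools. The PI's extra contamination on awareness is therefore smaller than it first appears. What remains distinctive is the detailed content on risks and desired behaviours, which bears on knowledge and the scenarios.

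Third, the contents page lists data management, data analysis and quality control sections whose text is not in this public version. Flagging of PI responses there cannot be ruled out. That limits any claim that the bias goes unhandled, but it does not withdraw the permission in 8.2.1.

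A reader might go further and infer that the PI knows the intended answers. The documents do not support that: no section says that the PI receives the annexes, and the annexes are described as questionnaires, not as scoring keys. Nor should the 12-of-150 case be read as a likely size.

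**Conclusion.** The point holds as a minor one. Section 8.2.1 expressly permits a respondent with prior exposure to the study content, 8.2.4 does not exclude that person, and random selection does not cure the exposure. This conflicts with the protocol's own reason for withholding its annexes.

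The effect on a country's result is about 1.2 points at the planned 85% correct if a PI takes part, and about 0.2 to 0.4 points in expectation. It approaches 4 points only with inclusion certain and true knowledge at an assumed 50%. These figures rest on one PI per country, a PI who is always correct, and the protocol's coverage figure standing in for the chance of inclusion. None of them would overturn a conclusion drawn at a margin of error near 20%. The case for change is that the bias favours the tools on two primary endpoints and is nearly free to remove. It is a cheap improvement, of minor severity, held with medium confidence because the PI's sight of the questionnaire is inferred.

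**What to change.** Delete from section 8.2.1 the clause "who may also take part in the survey if randomised alongside all other participants". Add to section 8.2.4 that country principal investigators for this study are excluded as HCP respondents.

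The cost is about one HCP per country leaving the sampling list. The repeat randomisation in section 8.2.2, which continues until quotas are met, already replaces that name. A broader exclusion of every HCP who has seen any study document is not needed on what the protocol describes, and it could cost more in pools that are expected to be small. If a PI's participation cannot be avoided in some country, flag the response and report the results with and without it.

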8.2.2 Inclusion Criteria

HCPs (including nurses and pharmacists in appropriate European markets) will be considered for participation in the survey if they are involved in the care of patients with paediatric bipolar I mania who receive ABILIFY[®].

Otsuka or Lundbeck (co-marketers of ABILIFY®) affiliates will provide lists of European HCPs involved in the care of patients with paediatric bipolar I mania being treated with ABILIFY®. For Ireland, this will be provided by BMS.

HCPs will be approached and asked to participate in the surveys through an email invitation from Pope Woodhead (PW). Prescribing physicians will be invited to refer non-prescribing colleagues (i.e. specialist nurses and pharmacists) to complete the survey where appropriate. These additional HCP types will be added to the original lists provided by the affiliates. Patients / Caregivers will be recruited by their HCPs.

PW will use the lists of HCPs to create quotas of target participants (Psychiatrists, Child / Adolescent psychiatrists, Nurses, and Pharmacists) who have expressed an interest in participating, who will be selected for participation using random number generator (RNG) software. Each of these lists will account for HCPs that are known to have been provided with the RM tools in each country. To ensure that sufficient HCPs are recruited (example given here is for larger countries), initial affiliate lists will be randomised to provide a target list of 50 participants. Of these 50 participants, it is intended to aim to recruit approximately 13 HCPs.

Recruitment will take place using invitation letters that will clearly identify the objectives of the study, the inclusion and exclusion criteria, and the expectations required of the HCP participants (e.g. an active role in patient recruitment).

If the recruitment target is not reached, the initial larger HCP lists (minus the 50 HCPs already approached) will be re-randomised to provide a further list of potential participants, who will then be approached in a similar fashion, and invited to participate accordingly. This process will continue and, if necessary, repeat until the required recruitment quotas are attained. A similar approach will be used to recruit in the medium and smaller sized markets.

HCPs will receive an honorarium (see below), which is payable only on survey completion, which compensates the HCPs for the time taken to participate in the survey and for providing PW with lists of patients / caregivers who will be randomised as part of the selection process. PW will be responsible for providing HCPs with access to the web-based survey by providing a web-link and a unique HCP identifier.

If survey drop-outs rates are high, or recruitment rates are low, recruitment will continue until the required numbers of surveys have been completed. The sampling method will also ensure that, for selected markets, specialist nurses and pharmacists who are involved in the care of patients on ABILIFY[®] (used for the adolescent bipolar I mania indication) are included as potential survey participants.

This approach is designed to both select HCPs and account for low response rates (e.g. a response rate of approximately 30%).

It should be noted that, in all countries involved in the study, ABILIFY® for the adolescent bipolar I mania indication will not be actively promoted. Hence, the pool of HCPs involved in treating these patients is expected to be small.

This approach should cover at least 20 to 30% of those who actively prescribe ABILIFY[®] for the adolescent bipolar I mania indication, which is anticipated to result in margins of error of < 20%, with confidence intervals in all countries of 95%, assuming 85% correct responses to knowledge based questions⁽⁵⁾.

The selection of the < 20% margin of error is driven by the small pool of HCPs treating patients within the adolescent bipolar I mania indication, and has been considered acceptable for similar evaluation of RM effectiveness surveys.

Bias will be avoided by random selection from a preliminary list, ensuring balance between the groups of Psychiatrists, Child / Adolescent Psychiatrists, Nurses and Pharmacists. To ensure that representatives from each target group are included in the study, the target lists will contain quotas of each subject type (e.g. 70 to 80% psychiatrists, 10 to 20% Nurses (if involved in treatment), and 5 to 10% pharmacists (if involved in treatment).

Random selection will then be carried out on each of the HCP types in order to generate lists containing appropriate proportions of each group. This approach will reduce the chances of significant selection bias (defined as particular HCP groups being favourably selected).

HCPs will be expected to complete the surveys within one month of being recruited. Patient and caregiver recruitment will occur through the HCPs. To ensure an unbiased sample, up to three patients / caregivers can be recruited through a single HCP. It is, however, expected that most HCPs will recruit one or two patients / caregivers only. The prescribing physician will recruit consecutive patients / caregivers, and informed consent (via a letter provided as part of the recruitment process) will be taken once potential participants are randomly selected from the HCP lists submitted to PW. Assent will be taken from paediatric patients who are not old enough to give informed consent, and appropriate consent will be taken from parents / carers, as appropriate.

In order to minimise bias of selecting compliant patients, PW will randomly identify actual participants from lists of patients supplied by HCPs. A similar quota based methodology as used in HCP selection will be employed when recruiting patients and caregivers (e.g. recruitment continues until the target quota has been reached or exceeded). Patients and caregivers will be provided with an invitation letter (containing informed consent, and details of the survey and how to participate) through their HCP. The HCP will pass contact details of those patients and caregivers agreeing to take part to PW who will provide unique IDs and the web-link to a patient survey).

The Patient / Caregiver surveys will be answered either whilst the patient is still receiving ABILIFY® or within 2 months of receiving their last dose (this is to reduce risks of patients / carers not being able to recall aspects of treatment and use of the RM tools), and within 1 month of being recruited.

Question 3 in the Patient / carer survey asks how long the patient was treated for, and if they are still being treated. Question 2 asks how old the patient was at treatment initiation. PW will also administer the web questionnaires and collect results from the patients and caregivers.

A total sample size of 148 to 158 HCPs and 148 to 158 patients / caregivers, as discussed below, will be met.

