3.8 Study Size

Sample size is based upon an acceptable margin of error defined as less than 20% in the population of interest, with a significance level of < 0.05, and a correct response distribution to a knowledge-based question of 85%. This is anticipated to yield between 148 and 158 HCPs, and 148 to 158 patients participating, once the final evaluation has been completed.

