8.5 Study Size

The sample size will be driven by the estimated size of the population receiving ABILIFY[®] for the adolescent bipolar I mania indication. The sample size is based on an acceptable margin of error of less than 20% in the population of interest. This will yield between 148 to 158 HCPs and 148 to 158 patients / caregivers once the final evaluation has been completed.

The calculation to determine sample size was performed using a sample size calculator available from Raosoft⁽⁶⁾, and incorporated margins of error by country; hence, the range of 148 to 158 HCPs and 148 to 158 patients / caregivers. The calculation of sample sizes is described in Section 9.7.2.

To achieve a representative population of HCPs relevant to the local clinical practice of the country (e.g. nurses, ancillary HCPs and prescribers), and patients and caregivers, and to attain the ranges outlined above, approximately 20 to 30% of the actually prescribing / treating HCP

population would need to be invited as part of the recruiting process. For example, in the UK (estimated HCP population of 2188), a confidence level of 95% and 85% of correct responses to a knowledge based question, and a sample size of 13 HCPs, gives a margin of error of 19.36% (see Table 9).

It should be noted that ABILIFY[®] used in this indication is considered an area of specialised medicine. It is expected that some countries will have few prescribers, especially so since the product will not be actively promoted for use in the paediatric / adolescent population. The actual numbers surveyed will depend on the specific numbers of centres and HCP users. These values may be adjusted accordingly if there are particularly high or low national usages of ABILIFY[®] for the adolescent bipolar I mania indication at the time of the survey.

The following numbers of HCPs, and Patients or carers will be included per country:

UK	13 HCPs and 13 Patients / caregivers
Germany	13 HCPs and 13 Patients / caregivers
Spain	13 HCPs and 13 Patients / caregivers
Italy	13 HCPs and 13 Patients / caregivers
Sweden	13 HCPs and 13 Patients / caregivers
Denmark	13 HCPs and 13 Patients / caregivers
Norway	12 HCPs and 12 Patients / caregivers
Ireland	12 HCPs and 12 Patients / caregivers
Austria	12 HCPs and 12 Patients / caregivers
Portugal	12 HCPs and 12 Patients / caregivers
Cyprus/Greece	12 HCPs and 12 Patients / caregivers
Slovenia	12 HCPs and 12 Patients / caregivers

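### The stated 20 to 30% coverage of prescribers does not fit the UK figures, and a margin below 20% in all countries is not secured at 12 to 13 respondents per country

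*Protocol*

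**What the plan says.** Two linked claims are made about each country's sample.

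- **Coverage.** Section 8.2.2: "This approach should cover at least 20 to 30% of those who actively prescribe" the product in this indication. Section 8.5 gives the same range as the share to be invited: "approximately 20 to 30% of the actually prescribing / treating HCP" population. For larger countries, section 8.2.2 says that "initial affiliate lists will be randomised to provide a target list of 50 participants", from which about 13 HCPs are to be recruited. Further lists are drawn if the quota is missed, and a response rate of about 30% is given as an example.
- **Margin.** Section 8.2.2 says of the coverage just described: "which is anticipated to result in margins of error of < 20%, with confidence intervals in all countries of 95" per cent. Section 8.5 supplies the worked case. It puts the number of UK HCPs at 2188, takes 85% of knowledge answers to be right, works at the 95% level, and reports the result thus: "and a sample size of 13 HCPs, gives a margin of error of 19.36" per cent.

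The country list in section 8.5 gives six rows 13 HCPs and 13 patients / caregivers. The other six (Norway, Ireland, Austria, Portugal, Cyprus/Greece, Slovenia) get "12 HCPs and 12 Patients / caregivers". The total is 6 × 13 + 6 × 12 = 150 per respondent group.

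**The concern.** The UK population and the UK list size stand in the same protocol and are far from the stated coverage. The coverage is also presented as the source of the precision, which it is not. The margin is claimed for all countries, but it is worked out only for a country with 13 respondents. It also uses a formula that performs poorly when about two incorrect answers are expected.

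The results go to the EMA, may lead to changes in the EU-RMP (section 6), and are presented by country with 95% confidence intervals (section 3.9). A reader who takes both statements at face value would think each national sample much more representative, and somewhat more precise, than it is.

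**Working it through.** **Inputs.** p = 0.85 and 95% confidence (sections 3.8, 8.2.2, 8.5); UK population N = 2188 and n = 13 (8.5); n = 12 in six rows (8.5); first list of 50 and response of about 30% (8.2.2).

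**1. Reproduce the plan's figure.** Normal-approximation half-width with finite-population correction:

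E = 1.96 × √(p(1−p)/n) × √((N−n)/(N−1))

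n = 13, N = 2188: 1.96 × √(0.1275/13) × √(2175/2187) = 19.36%. It matches. Without the correction it is 19.41%, so at p = 0.85 the formula stays below 20% for any N.

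**2. Same formula at n = 12.**

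| N | E |
|---|---|
| no correction | 20.20% |
| 2188 | 20.15% |
| 1000 | 20.09% |
| 600 | 20.02% |
| 500 | 19.98% |
| 250 | 19.75% |
| 100 | 19.05% |

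The margin is below 20% only for N of about 551 or fewer.

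**3. Coverage.**
- 20% and 30% of 2188: 438 and 656 HCPs.
- First list: 50/2188 = 2.3%. Recruited: 13/2188 = 0.6%.
- Expected yield of one list at 30% response: 50 × 0.30 = 15, already above the target of 13.
- Lists needed to reach the stated range: 438/50 to 656/50, about 9 to 13.
- Pool of which 50 would be 20 to 30%: 50/0.30 to 50/0.20 = 167 to 250.

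**4. Does coverage drive the margin?** With n fixed at 13, E is 18.7% at N = 167, 18.9% at N = 250 and 19.4% at N = 2188. A list of 50 goes from 30% of the pool to 2.3% while the margin moves by 0.7 points. The margin depends on n and p.

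**5. Is the nominal 95% real at this size?** Expected incorrect answers: 13 × 0.15 = 1.95. For 11/13 the normal-approximation interval runs to about 104%. Summing binomial probabilities over the results whose interval contains 0.85 gives true coverage of 87.2% (n = 13) and 85.3% (n = 12). Most of the loss comes from all-correct results, which give an interval of zero width: 0.85^13 = 12.1% and 0.85^12 = 14.2%.

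**6. Intervals suited to small n.**

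| Result | Method | 95% interval | Half-width | Reach below estimate |
|---|---|---|---|---|
| 11/13 | Clopper-Pearson | 54.6 to 98.1% | 21.8 | 30 points |
| 11/13 | Wilson | 57.8 to 95.7% | 19.0 | 27 points |
| 10/12 | Clopper-Pearson | 51.6 to 97.9% | 23.2 | 32 points |
| 10/12 | Wilson | 55.2 to 95.3% | 20.1 | 28 points |

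**7. Pooled sample.** n = 150, p = 0.85: 1.96 × √(0.1275/150) = ±5.7 points, before any allowance for clustering.

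**The case against.** The strongest reply is that the margin claim is largely met on its own terms. The 19.36% is correct by the stated method, so the six countries with 13 respondents satisfy it at 85% correct. A margin of error is a half-width, and the Wilson half-width at 11/13 is 19.0, still under 20. Section 8.5 says the calculation took account of country and points to Table 9, which is not in the public text. If the six smaller countries have populations of about 551 or fewer, they satisfy the formula too, and otherwise the overshoot is at most 0.2 points. Section 8.2.2 says the margin is anticipated, states the 85% assumption, and explains why a wide margin was accepted. All of this stands, and it limits the margin point to one of wording and method.

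On coverage, 50 is a first list given as an example, and further lists are drawn until the quota is filled. It is therefore not a cap. But at about 30% response the first list normally suffices, so redrawing would not plausibly reach 438 to 656. The 2188 may be a broader group than active prescribers, since section 8.2.2 expects a small pool. The protocol does not say so, and section 8.5 uses 2188 directly after the 20 to 30% statement. Since 13/50 = 26%, the range may be a recruitment yield mislabelled as population coverage, but that is inference.

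A reader might go further in four ways that the document does not support:

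- That reported intervals will be too narrow or pass 100%. The formula appears only as a planning calculation, and the interval method for reporting is not shown in the public text.
- That awareness and usage endpoints break the promise because margins near 50% are 27 to 28 points. The margin is tied to knowledge questions at 85% correct, and none is claimed for those endpoints.
- That splitting 12 or 13 into patients and caregivers within a country makes the claim fail. Section 3.9 does not say these breakdowns are crossed.
- That "148 to 158 patients participating" in section 3.8 is a different sample-size target. Sections 8.2.2 and 8.5 give the same number for patients and caregivers together, so this is a clerical slip.

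**Conclusion.** The concern holds in a limited form, as a should-fix.

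- **Coverage is contradicted by the protocol's own UK example:** 2.3% on the first list and 0.6% surveyed, against 20 to 30% stated. This rests on 2188 being the relevant population, as section 8.5 presents it. If it is not, the text needs to say what the relevant pool is.
- **Coverage does not yield the margin.** The link drawn in section 8.2.2 is wrong.
- **A margin under 20% in all countries is not secured.** It is met on paper at n = 13. At n = 12 it depends on populations not shown here. At both sizes the nominal 95% is nearer 85 to 87% when 85% answer correctly. With exact intervals the half-width exceeds 20 points at 11/13 and 10/12, and the lower limit lies about 30 points below the estimate.

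It would be wrong to conclude that the margin fails in every country, that failure at n = 12 has been shown, or that the sample must be enlarged.

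**What to change.** Revise the wording of sections 3.8, 8.2.2 and 8.5 and leave the sample size as it is.

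1. Delete the 20 to 30% coverage statement, or restate it per country from actual counts of HCPs listed, invited and recruited. Say whether 2188 is all HCPs or active prescribers. Remove the claim that coverage leads to the margin.
2. Replace the all-countries margin with: about 20 points by normal approximation, at 85% correct on knowledge questions; with small-sample (Clopper-Pearson) intervals, about 55 to 98% at 11/13 and 52 to 98% at 10/12.
3. Use Wilson or Clopper-Pearson for country-level intervals, if the unpublished analysis section does not already do so.
4. Treat country results as descriptive and rest conclusions on the pooled sample of about 150 per respondent group: about ±5.7 points at 85%, before clustering.
5. In section 3.8, write patients and caregivers combined.

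The cost is text only. No participants, data items or timelines change. The one drawback is that the stated precision and coverage become less favourable.
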